5. RESEARCH OBJECTIVES

- 1) To compare plasma levels, biopsy mRNA (using low density expression arrays) and protein (using either Luminex or Western blotting) levels of the following parameters between IBD patients treated with Frondanol and those treated with placebo at baseline and after six months of treatment:
 - a) Cytokines: TNF α , IL1 β , IL6, IL17A, IL21, IL22, IL23, IFN γ , IFN α , as well as vascular endothelial growth factor (VEGF-A), MIP-1, MIP-2;
 - b) Markers of inflammation: Myeloperoxidase, calprotectin, S100A12, β 2-microglobulin, amyloid A (A-SAA), intercellular adhesion molecule 1 (ICAM-1), vascular cell adhesion molecule 1 (VCAM-1), MIP-2 α (CXCL2), MCP-1 (CCL2). Leukotriene B4 (LTB4), 5-hydroxyeicosatetraenoic acid (5-HETE) and prostaglandin E2 (PGE2) will be measured by specific ELISA assays.
- 2) To compare the following routine clinical parameters between IBD patients treated with Frondanol and those treated with placebo at baseline and after six months of treatment:
 - a) Patient symptoms;
 - b) Blood: Complete blood count (CBC), erythrocyte sedimentation rate (ESR), C-reactive protein (CRP), albumin;
 - c) Stool: Fecal calprotectin level;
 - d) Endoscopic and histologic features.
- 3) To compare in-vitro concentration-dependent responses to Frondanol and placebo on inflamed organoids by measurement of cytokines and other inflammatory markers, in particular 5-HETE, LTB4 and PGE2.

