6.3 Sample and recruitment

All eligible IBD patients visiting Gastroenterology Department of any of the study centres that will participate in patient recruitment (Mediclinic City Hospital, Mediclinic Parkview Hospital and Rashid hospital) under the care of any of the coinvestigator consultant gastroenterologists during the period of recruitment (12 months from the start date of the study – to be decided following ethical approval) will be offered to take part in the study.

Block randomization over four blocks of 25 patients will be used to ensure an equal number of patients in each treatment group, even if the trial was terminated early for any reason. Two blocks will be reserved for patients with quiescent/minimal disease and two blocks for patients with mild disease, in order to ensure an equal number of these patients in each treatment group. Patients will be randomised (1:1) to receive Frondanol (one 1000 mg capsule twice daily) or placebo (in a similar capsule) as an adjunct to their standard therapy using a randomization number sequence generator. This will be conducted by the study statistician using the Microsoft Excel random number generator and will only be shared with the study coordinator.

All patients and investigators, excluding the study coordinator, will be blinded to treatment allocation. Frondanol and placebo capsules will be placed in identical-looking vials which will be labelled with the study name and number, and no identifying information. The labelling of the vials will be done with the open randomization sheet by the study coordinator. When a patient agrees to participate, and signs the informed consent form, the physician will assign to the patient the next available randomization number from the randomization sheet (supplied by the study coordinator) with the corresponding labelled medication vial. Patients will be instructed to take one capsule of their assigned medication twice daily. Hence, capsules will be given in a double-blind manner where patient and physician are not aware of treatment allocation as the treatment and placebo vials will only indicate the pilot study name. Investigators involved in the laboratory analysis of samples will also be blinded, they will only know if a patient belongs to group 1 or 2 but will not know which group is taking Frondanol and which is taking placebo.

RJ

Version 3.2. Effective Date: 04 December 2021

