6.13 Subject Identification

All patient data and specimen will be de-identified and coded with the unique study number of the patient. The code linking the study number with the patient will be accessed by the study coordinator only and maintained at MBRU in a database and will not be provided to the PI or her research team. Patient data will be collected using protocol-specific case report forms (CRFs), which will be used to create electronic CRFs (e-CRFs). Clinical records for all patients, including CRFs, will be retained by the PI in a secure storage facility for ten years after the completion of the study. Paper data will be stored in a locked

RJ

Version 3.2. Effective Date: 04 December 2021

cabinet and electronic data will be stored on a password-protected computer in the custody of the PI. The data linking patient identifying information and their de-identified data will be in the custody of the study coordinator who will be unblinded. All patients will complete the following study visits: Screening (medical history, physical examination, vital signs and standard of care tests including blood and stool tests), baseline endoscopy (day 1 of treatment, date to be agreed between the gastroenterologist and patient), 3 months (routine monitoring with standard of care tests including blood and stool tests), 6 months (second endoscopy and standard of care tests including blood and stool tests).

 -
RJ

Version 3.2. Effective Date: 04 December 2021

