6.14 Study schedule

Table 1: Variables to be collected from participants

Method of data collection	Variables
Questionnaires	Mayo Score, IBDQ
Medical record	Symptoms
Blood samples	Routine blood tests as well as an extra sample (10 mL) for research purposes will be obtained at T0 (start of study), T1 (3 months) and T2 (6 months).
Stool samples	Routine stool sample will be collected for measurement of fetal calprotectin levels at the recruiting hospital at T0, T1 and T2.
Tissue samples	Colonoscopies will be performed as part of the routine clinical practice and these include acquisition of routine biopsies, typically 10-15 from each patient. A few additional biopsies (2-4) will be collected for our studies during routine colonoscopies when these are performed, then they will be snap frozen and analyzed in MBRU research laboratory facilities.

Table 2: Schedule of Activities

Variable	Visit # 1 (T0)	Visit # 2 (T1 – 3months)	Visit # 3 (T2 – 6 months)
Questionnaires	Mayo Score, IBDQ	Mayo Score, IBDQ	Mayo Score, IBDQ
Medical record	Symptoms	Symptoms	Symptoms
Blood samples	Routine blood tests as well as an extra sample (10 mL) will be obtained, stored and analyzed in MBRU research laboratory facilities.	Routine blood tests as well as an extra sample (10 mL) will be obtained, stored and analyzed in MBRU research laboratory facilities.	Routine blood tests as well as an extra sample (10 mL) will be obtained, stored and analyzed in MBRU research laboratory facilities.
Stool sample	Routine stool sample will be collected for measurement of fetal calprotectin levels at MCH	Routine stool sample will be collected for measurement of fetal calprotectin levels at MCH	Routine stool sample will be collected for measurement of fetal calprotectin levels at MCH
Tissue samples	If colonoscopy is performed for routine clinical practice at the start of the study, a few additional biopsies (2-4) will be collected for our studies, snap frozen and analyzed in	No tissue samples collected	If colonoscopy is performed for routine clinical practice at the end of the study, a few additional biopsies (2-4) will be collected for our studies, snap frozen and analyzed in

RJ

Version 3.2. Effective Date: 04 December 2021

	MBRU research laboratory facilities.	MBRU research laboratory facilities.
--	--------------------------------------	--------------------------------------

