8.2 Statistical methods

All statistical analyses will be carried out using SPSS Software (Armonk, New York, USA). Potential confounders such as age and sex will be controlled for during the analysis phase. A per-protocol analysis including only participants who have a full data set will be used to assess the efficacy of Frondanol treatment in lowering inflammatory markers. An intention-to-treat analysis will also be conducted including patients who drop out before the study ends, for whom we will use last observation carried forward (LOCF) i.e. we will impute the last observed data for all subsequent (missing) observation points. For quantitative data, within-group and between-group comparisons will be analyzed using the General linear Repeated Model (MANOVA), which would allow for adjustment of potential confounders such as age and sex. Data will be plotted as mean \pm SEM and p values <0.05 will be considered statistically significant.

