10.3 Costs and Payments

Participants will not receive study incentives (compensation) nor will they incur costs for participating in this study.

10.4 Safety Monitoring:

In the unlikely event that side effects occur, patients will be requested to immediately inform the study coordinator/research nurse, PI or consultant gastroenterologist. A direct phone number will be given to patients so that they are able to call the study coordinator or assigned nurse in case of any adverse events. Depending on the severity of the event, the participant will be instructed whether to report to the Gastroenterology unit at the study site or to head to the emergency department of one of the hospitals covered by the trial's liability insurance, for further investigation and possible treatment.

Simultaneously, the PI, assisted by the clinical gastroenterologists on the team, and taking into account any other medical information available, will perform a causality assessment to ascertain whether the adverse event was related to participation in the trial. If the adverse event is deemed to be related to participation in the trial, the participant will be advised to immediately stop taking the study medication (whether Frondanol or placebo) and will be provided with the necessary medical care until the issue is resolved.

In the unlikely event that the adverse event is deemed to be caused by Frondanol and if the assessment by the study team results in a doubt that further adverse events may occur with other participants, the trial will be immediately suspended, and all participants will be informed and required to stop taking their assigned study medication and await further instructions from the PI or trial coordinator.

Any serious or unexpected adverse event will be reported by the PI to all ethical committees that have approved this study, no later than 24 hours for

RJ

Version 3.2. Effective Date: 04 December 2021

life threatening events and no later than 10 working days for non-life-threatening events. Reports to the involved ethical committees will include advice from PI as to whether in her opinion (supported by the opinions of the study team's gastroenterologists):

- The adverse event was related to the protocol or the study drug
- The adverse event necessitates an amendment to the study protocol and/or patient information/consent form

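### Section 6.3 gives laboratory investigators each patient's group label (1 or 2) with no stated need and no stated release time; it should be withheld until assay results are locked

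*Combined protocol and SAP*

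**What the plan says.** Section 6.3 masks patients and all investigators except the study coordinator. It describes the laboratory investigators as blinded too, with this qualification: "they will only know if a patient belongs to group 1 or 2 but will not know which group is taking Frondanol". The study statistician generates the sequence and shares it only with the coordinator.

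Section 6.13 states: "All patient data and specimen will be de-identified and coded with the unique study number of the patient". Section 9.1 says that study data are held under the subject number only.

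Objective 1 in section 5 compares plasma and biopsy markers "between IBD patients treated with Frondanol and those treated with placebo at baseline and after six months of treatment". Table 1 in section 6.14 says that "an extra sample (10 mL) for research purposes will be obtained at T0 (start of study), T1 (3 months) and T2 (6 months"). Extra biopsies are taken only when a routine colonoscopy is done.

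Section 8.2 describes its per-protocol approach thus: "including only participants who have a full data set will be used to assess the efficacy of Frondanol treatment in lowering inflammatory markers". It adds: "An intention-to-treat analysis will also be conducted including patients who drop out before the study ends", with last observation carried forward (LOCF). For quantitative data, "within-group and between-group comparisons will be analyzed using the General linear Repeated Model (MANOVA").

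No section says why the laboratory should hold the group label, when it receives it, or whether assay results are locked first. No section describes a laboratory procedure for repeats or exclusions.

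**The concern.** A two-value label does not say which arm is active, but it does say which samples belong together. If staff hold it while producing results, samples could be batched, repeated, read or excluded by group, even unintentionally. The label also makes the masking depend on a single disclosure: once the arm of one patient is known, so is the arm of everyone on the list.

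This matters because section 8.2 judges efficacy by the lowering of inflammatory markers, and this laboratory measures the objective 1 markers. The per-protocol set is the most directly exposed. Read literally, a patient with one voided and unreplaced result no longer has complete data and drops out. The LOCF analysis is described for patients who leave the study, so it may not cover a voided assay.

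**Working it through.** **1. Does the laboratory need the label?** Section 6.13 gives every specimen a unique study number, which is enough to track samples and pair visits. Sections 6.3 and 6.13 do not contradict each other. The label is simply additional to what the laboratory is shown to need.

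**2. How much is exposed (not shown to be affected)?**
- Objective 1a: 9 cytokines + VEGF-A, MIP-1 and MIP-2 = 12 items.
- Objective 1b: 9 markers + LTB4, 5-HETE and PGE2 = 12 items.
- Objective 2: symptoms (1), blood tests (4), fecal calprotectin (1), endoscopic and histologic features (2) = 8 items.
- Laboratory share: 24 of 24 + 8 = 32, or 23 of 31 if MIP-2 and MIP-2α are one analyte.
- Research blood samples for objective 1: up to 100 × 2 = 200, plus up to 100 at three months, plus any biopsies.

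The count does not show how much reader judgement each assay allows. Western blotting is only one of the listed protein options.

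**3. What does one disclosed allocation reveal?** With the group list, 100 − 1 = 99 further allocations follow. With study numbers only, none follows directly.

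**4. Illustration of selective voiding.** The plan gives no figure to reproduce, and every input except the 50 per arm is an assumption: normal data with unit variance, no true effect, and correlation r between baseline and six months. The k highest six-month readings in one group are voided and those patients are lost. The test is a two-sample t-test at two-sided 5% on six-month minus baseline, which equals the two-visit group-by-time test. Rejection rates from 100,000 simulated null trials per cell:

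| r | k = 1 | k = 2 | k = 3 | k = 5 |
|---|---|---|---|---|
| 0.3 | 5.4% | 5.9% | 6.8% | 9.0% |
| 0.5 | 5.3% | 5.8% | 6.3% | 7.8% |
| 0.7 | 5.1% | 5.4% | 5.9% | 6.7% |

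A repeat run agreed to within about 0.3 percentage points. Without voiding, the rate is 4.9% to 5.1%.

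Variants:
- Three-visit MANOVA group-by-time test: 5.1–5.3% (k = 1) to 6.4–8.6% (k = 5).
- LOCF of the three-month value into the voided reading: 5.1–5.3% to 6.5–8.6%.
- Between-group term averaged over baseline and six months: 5.7–5.8% to 12.9–15.6%.
- Voiding the largest changes instead of the largest six-month values (a stronger assumption), on the change test: 6.0–6.2%, 7.9–8.0%, 10.3–10.7% and 17.5–17.9% for k = 1, 2, 3 and 5.

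**5. Direction.** The excess favours whichever arm was trimmed. In the table's scenario at k = 5, rejections favouring that arm are 5.6% to 8.3%, against a nominal 2.5%. If staff do not know the active arm and either is equally likely to be trimmed, rejections favouring Frondanol are half the total: 5.1–5.4% ÷ 2 ≈ 2.6–2.7% at k = 1, and 6.7–9.0% ÷ 2 ≈ 3.4–4.5% at k = 5.

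**The case against.** The sponsor can fairly say that section 6.3 makes a deliberate, disclosed choice. The laboratory does not know which group takes Frondanol, so it cannot knowingly favour the product. The plan also does not say that the label arrives before the assays are finished. The illustration assumes conduct that no section describes, and with one or two voided six-month readings the change test barely moves. All of this stands. It limits the point to an avoidable weakness and a gap in timing.

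Three stronger readings are tempting, and the documents support none of them.

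- **That the laboratory is unblinded, or that the marker results are biased.** Section 6.3 keeps treatment identity masked, and nothing shows samples being handled differently by group.
- **That safety monitoring would break the code.** Section 10.4 provides for the case where "the adverse event is deemed to be caused by Frondanol", and a reader might infer that such a judgement discloses that patient's arm. It is an opinion on causality, not a revealed allocation. The same section has a participant stop study medication whichever arm they are in, and nothing says that assessors or laboratory staff are told the arm.
- **That the whole trial's masking is affected.** Patients, treating physicians and the routine objective 2 measures are not shown to be touched.

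The objection does not supply a reason for the laboratory to hold the label. Even if the sponsor means it to arrive only after the assays, the text does not say so.

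**Conclusion.** The point holds as a modest one. Section 6.3 gives the laboratory patient-level group membership that it has no stated need for, and leaves the timing open. If the label is available before results are final, the 24 laboratory items of objective 1 are open to handling by group, and the masking of all 100 patients rests on no single allocation becoming known.

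The size of any bias cannot be derived from the documents. The 5–9% and 6–18% ranges rest wholly on the assumed voiding in one group and the assumed correlations. They show a mechanism and do not estimate what will happen. The case for change is the asymmetry: the label has no stated benefit, and withholding it alters no sample size, power, significance level or patient procedure.

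**What to change.** Replace the sentence in section 6.3 with:

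> Laboratory investigators will receive specimens identified by study number only, in an order unrelated to treatment, and will not be given any group code until assay results, repeats and exclusions are locked. The study statistician and study coordinator, who hold the randomisation list, will not share it with the laboratory before that lock.

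The second sentence is needed because the statistician generates the sequence, so it is not enough to say that the code is released for analysis.

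The cost is minor sample-list preparation and a lock step by the coordinator, who is already unblinded. If the change is judged substantial, section 10.7 requires submission to the ethics committee before it is implemented. No extra staff or patient procedures are needed.

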6.4 Study population

One hundred patients (50 per arm) with stable IBD (Crohn's disease or ulcerative colitis, in remission) will be recruited in one of the participating study centres (Mediclinic City Hospital, Mediclinic Parkview Hospital, Rashid Hospital) by one of the coinvestigator consultant gastroenterologists.

6.5 Eligibility criteria

- **Inclusion criteria:**

A confirmed clinical diagnosis of IBD of any duration, age 18 years or older, with mild to moderate disease and on standard therapy. The diagnostic criteria for IBD include the presence of chronic diarrhoea for more than four weeks, and evidence of active inflammation on endoscopy and chronic changes on biopsy. Patients with stable mild to moderate IBD will be eligible for the study. Stable IBD is defined as having stable symptoms over a period of several weeks, diagnostic evaluation has been completed and the patient has been on consistent medication. Mild to moderate IBD is indicated by a Partial Mayo score (Mayo Clinic Score/Disease Activity Index for Colitis) of between 1-6, and a total of Mayo score of 1-10 (Pabla and Schwartz, 2020). For patients with Crohn's disease, only those with Crohn's colitis will be included (patients with small bowel disease are eligible to enter the trial as long as they also have large bowel inflammation).

- **Exclusion criteria:**

Pregnancy, breastfeeding, allergy to seafood or marine products, severe medical illness such as uncontrolled diabetes ($\text{HbA1C}>10$), significant or unstable cardiovascular or pulmonary disease, impaired renal function ($\text{Cr}>2.0\text{mg/dL}$), current or recent (<1 year) malignancy, or other significant medical illness that in the view of the investigators may impair participation in the study. Patients with severe IBD (defined by a Partial Mayo score of 7-9 and a total Mayo score of 11-12 (Pabla and Schwartz, 2020), with active symptoms) will not be eligible to participate in the study.

Reference:

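### Mayo bands taken from an ulcerative colitis review define severity for Crohn's patients too, and on the usual item structure the severe-disease exclusion cannot apply to anyone without rectal bleeding

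*Combined protocol and SAP*

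**What the plan says.** Section 6.5, repeated in the protocol summary (section 1), states: "Mild to moderate IBD is indicated by a Partial Mayo score (Mayo Clinic Score/Disease Activity Index for Colitis) of between 1-6". For the full score, the same sentence sets the limit with the words "and a total of Mayo score of 1-10". The exclusion reads: "Patients with severe IBD (defined by a Partial Mayo score of 7-9 and a total Mayo score of 11-12", and adds active symptoms as a condition. Both definitions are worded for IBD as a whole. The reference given for them is titled "Assessing Severity of Disease in Patients with Ulcerative Colitis".

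The same section admits Crohn's disease: "For patients with Crohn's disease, only those with Crohn's colitis will be included". A bracketed note then widens this: "patients with small bowel disease are eligible to enter the trial as long as they also have large bowel inflammation". It gives no separate definition of mild, moderate or severe disease for these patients.

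In section 6.14, the questionnaire row of Table 2 reads "Mayo Score, IBDQ" at each of T0, T1 and T2, and Table 1 lists the same two instruments. Symptoms are also taken from the medical record at each visit. Neither table contains a Crohn's activity index.

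The design overview at the start of section 6, and section 6.4, describe the participants as being in remission. That condition is not among the section 6.5 criteria and is not defined.

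**The concern.** A severity rule should separate those who may enter from those who may not in each disease the trial enrols. Here a single index, sourced to one of the two diseases, does this for both. If the score cannot reach the severe band for an identifiable group, the exclusion exists on paper only for that group. The claim that the population is mild to moderate then rests on unstated clinical judgement.

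Two things are at stake. One is the purpose of the exclusion, which is to keep patients with severe disease out of a six-month placebo-controlled comparison. The other is interpretation: without a Crohn's measure at baseline or follow-up, the report cannot describe the activity of its Crohn's participants, or any change in it, on a scale meant for that disease.

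**Working it through.** The plan gives no figure to reproduce on this point, so the check applies its own bands to every possible score.

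**Inputs from section 6.5.** Eligible: partial 1-6 and total 1-10. Severe: partial 7-9 and total 11-12. The tops of the severe bands imply scale maxima of 9 and 12.

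**Assumption, not in the documents.** There are four items, each scored 0-3: stool frequency, rectal bleeding, physician global assessment and endoscopy. The partial score is the sum of the first three (3 x 3 = 9) and the total is the sum of all four (4 x 3 = 12). Both agree with the implied maxima.

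**Maxima for a given bleeding score b.** Maximum partial = 3 + 3 + b = 6 + b. Maximum total = 3 + 3 + 3 + b = 9 + b.

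| Bleeding score b | Max partial | Max total | Severe definition (partial ≥ 7 and total ≥ 11) reachable? |
|---|---|---|---|
| 0 | 6 | 9 | No, on either part |
| 1 | 7 | 10 | No, total falls short |
| 2 | 8 | 11 | Yes |
| 3 | 9 | 12 | Yes |

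**Enumeration.** There are 4 x 4 x 4 x 4 = 256 item combinations. Five meet the severe definition as written: the one with every item at 3 (total 12) and the four with exactly one item at 2 (total 11). None of the five has bleeding below 2.

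With bleeding fixed at 0 there are 4 x 4 x 4 = 64 combinations. None is severe, even if either part of the definition were enough. Sixty fall inside the eligible bands. The other four have a partial score of 0 (stool frequency and global assessment both 0, with any of the four endoscopy values), so they fail at the bottom of the scale, not the top.

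The case b = 1 differs slightly. The severe definition cannot be met, but a partial score of 7 is possible and would fail the inclusion limit of 6. Only at b = 0 do the inclusion ceiling and the exclusion both have no effect.

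These are counts of score patterns, not proportions of patients.

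**Do other entry conditions limit severity?** Section 6.5 defines stable disease by steady symptoms over several weeks, a finished diagnostic work-up and unchanged medication. Severe disease that does not change can satisfy all three. Investigator discretion in the exclusion list concerns other significant medical illness, not the severity of the IBD. Remission would limit severity, but it is missing from section 6.5 and sits badly with admitting a partial score of up to 6.

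**The case against.** The strongest reply has several parts.

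- *The ceiling is not specific to Crohn's disease.* This stands. The arithmetic covers any patient with a bleeding score of 0, including one with ulcerative colitis, and the documents do not say how many Crohn's participants lack bleeding. What is specific to Crohn's disease is that the bands come from an ulcerative colitis source and no other severity measure is offered.
- *Crohn's entry is limited to colonic disease, so a colitis index is a deliberate choice.* This is partly right, but additional small bowel disease is allowed and the plan does not explain the choice.
- *Stability and remission keep severe patients out.* In practice they may reduce the number. As written, stability does not limit severity and remission is not an entry criterion.

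A reader might also infer more than the documents support.

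- *That the symptom comparison in objective 2 is compromised, or that symptom change is poorly measured.* The objective, whose opening words are "To compare the following routine clinical parameters between IBD patients treated with Frondanol and those treated with placebo at baseline and after six months of", lists symptoms without naming an instrument. IBDQ and medical-record symptoms are collected at all three visits.
- *That pain or small bowel change cannot move the Mayo score.* The documents do not list the items, and a physician global rating, if present, could respond to either.
- *That a stated percentage of the treatment effect is lost.* This would need the Crohn's share of the 100 patients and the share of their change that Mayo captures. Neither is given, and pooled Mayo change is not a named endpoint.
- *That the randomisation strata are wrong.* Section 6.3 does not tie them to Mayo cut-offs.

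**Conclusion.** The concern holds as an eligibility and measurement gap. Severity for all IBD is defined by Mayo bands from an ulcerative colitis source, Crohn's patients are enrolled, and no Crohn's activity index is collected. On the assumed four-item, 0-3 structure, a patient without rectal bleeding can reach at most 6 partial and 9 total, against severe thresholds of 7 and 11, so the exclusion cannot apply to that patient. The ceiling depends on that assumption. The absence of a Crohn's severity definition does not.

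The number of patients affected cannot be estimated from the documents. The main efficacy analysis is not directly touched, because section 8.2 directs it at inflammatory markers. The change should still be made before enrolment: eligibility cannot be repaired afterwards, and baseline scores that were never collected may not be recoverable.

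**What to change.** 1. In section 6.5 and the protocol summary, define mild to moderate and severe disease for Crohn's patients by a validated Crohn's activity index. The index and its cut-offs are for the investigators to choose.
2. Reconcile that definition, and the Mayo bands, with the remission wording in the design overview and section 6.4.
3. In Tables 1 and 2 of section 6.14, add the chosen index for Crohn's patients at T0, T1 and T2.
4. In section 8.2, report Mayo change in ulcerative colitis and the Crohn's index in Crohn's disease, and name IBDQ, already collected in everyone, as the pooled patient-reported measure.

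The cost is a few minutes at visits already scheduled, with no new procedure or staff. The drawback is that activity is analysed by disease, so each of those analyses has fewer than the 100 patients.
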